### 5 Study Design

This interventional clinical trial is a prospective, single center, randomized controlled study. Patients being treated for their glaucoma at BMC's Yawkey Eye Clinic will be selected. Patients will be randomly placed, without manipulations by the principle investigator or any member of the research team, on one of the drop aid devices (including Fabrication Autodrop Eye Drop Guide, Simply Touch Eye Drop Applicator, Owen Mumford OP 6100 Autosqueeze), in addition to a no drop aid control, for a total of 4 groups.

Subjects have an equal chance of being randomized to one of the following study arms:

- Arm A: No intervention – Control
- Arm B: Active Comparator- Eye Drop Aids Including:
  - Simply Touch Eye Drop Applicator
  - Fabrication Autodrop Eye Drop Guide
  - Owen Mumford OP 6100 Autosqueeze

The primary endpoint is the comparison of baseline IOP measurement and follow-up IOP measurement. This comparison will determine the efficacy of using a drop aid. The secondary endpoints include the precision of the drop aid, patient satisfaction, and their likelihood to use a drop aid outside of the study. Data collection for assessment of study objectives will be obtained via standard of care clinic visits and completion of study diary and satisfaction survey by the patient with assistance of research team, if needed.

See the Appendix section 15.1 for a schematic of the study design and section 15.3 for drop aid labels and instructions.

### 6 Potential Risks and Benefits

#### 6.1 Risks

Risks and possible discomforts involved with study participation are associated with eye dropper use and the possibility of a breach of confidentiality. The use of the assigned drop aid does not pose any additional risk to subjects from only using an eye drop bottle for administration. Both methods of eye drop administration pose the same risk of corneal abrasion or infection from poking the eye with the device/bottle, or using a dirty device/bottle. Subjects will be advised by the investigator on how to decrease these risks when administering drops with the assigned device.

There is the unlikely possibility of breach of confidentiality. Confidentiality will be protected as stated in Section 11.1 of this protocol.

#### 6.2 Unknown Risks

There may be unknown risks or discomforts involved. Study staff will update all subjects in a timely manner with any new information that may affect their health, welfare, or decision to participate in this study.

### 6.3 Potential Benefits

Study participants may benefit from participation by improved eye drop compliance, decrease in medication refill requirements, receiving a drop aid at no cost, and an overall increased satisfaction with eye drop medications. It is also possible that subjects may not receive any direct benefit from participation, but they will be helping investigators learn about the benefits of drop aids as well as better understand the efficacy of its usage for patients at BMC.

### 6.4 Analysis of Risks in Relation to Benefits

The project allows for potential improvement in patients' medication compliance. These drop aids are designed to help deliver only the necessary amount of medication and target the eye to allow for easier delivery of medications. The drop aids involved in this study are targeted toward improving patient experience when using glaucoma medications. This may reduce patient frustration and increase adherence to medication allowing for better glaucoma treatment outcomes. The risks of this study include a minimal risk of loss of confidentiality. The risk is minimal in comparison to the potential benefits of: improved medication compliance, monetary benefits of decreased number of refills, increased patient satisfaction with eye drop medications, and community benefit of understanding the effectiveness of drop aids.

## 7 Study Subject Selection

### 7.1 Subject Inclusion Criteria

In order to be eligible to participate in this study, an individual must meet all of the following criteria:

- Age 18 years or older
- Currently on the same topical medication for treatment of glaucoma for a minimum of two months
- Patient of Boston University Eye Associates
- Agrees to use the drop aid with each delivery, return to the clinic after approximately 6 weeks of using the drop aid, document completion of medication drops, and fill out survey at the end of the 6 weeks

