### 3 Background/Rationale & Purpose

#### 3.1 Background Information

Glaucoma is a disease characterized by an increased intraocular pressure, resulting in damage to optic nerve. This disease can be diagnosed by measuring visual field loss, identifying other changes in the physical structures of the eye and by measuring IOP. If untreated, glaucoma can result in preventable vision loss.

Glaucoma is commonly treated with prescription eye drops. It is critical that patients receive the correct dose and frequency of eye drop medication as prescribed. This will prevent disease advancement and decrease the chances of vision loss. However, patient compliance with medication limits symptom improvement due to deliberate misuse, financial concerns, or unintentional issues in drug delivery. Some patients have difficulty putting in the correct amount of eye drops themselves. Common problems are from a patient missing their eye, delivering too much medication, or they are unable to squeeze the bottle properly. This can create further problems with pharmacy refills, as well as financially from buying an increased number of prescriptions. In order to ensure patients are receiving the correct amount of drops with each use, drop aids are available at local pharmacies for purchase. These are not commonly recommended because they can be costly and their usefulness has not yet been proven. Although if a drop aid proves to be effective, they may result in a decrease of cost for the patient in the long term by allowing a decrease in premature completion of the bottle.

This study aims to determine the efficacy of glaucoma drop aids delivery of ophthalmic medications by improving medication compliance, visual function, and decreasing medication waste in the patient population at BMC.

This study will be conducted in compliance with the protocol, applicable regulatory requirements, and BMC/BU Medical Campus Human Research Protection policies and procedures.

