#### 3.2 Rationale and Purpose

The ophthalmology department at Boston Medical Center sees on average 275 glaucoma patients weekly, 80 percent of which are placed on glaucoma medications. It is critical for these patients to receive the correct dose and frequency of their eye drops, in order to prevent disease advancement and decrease the chances of vision loss. However, a majority of patients are unable to properly deliver the eye drops into their eyes due to poor vision or difficulty squeezing drop bottles. Furthermore, when patients are able to instill drops into their eyes, they often deliver more than a necessary amount, leading to premature completion of the bottle. This is an issue in the United States, as most glaucoma patients are on 2 to 3 different medication drops and Medicare Part D sponsors permit refills at only 70% of predicated days of use, accounting for about half of glaucoma patient population. Self-reported studies also showed that approximately 25% of patients reported problems with early exhaustion of eye drop bottles. The average size of a glaucoma medication bottle is around 10 cc and these medications, when used 2 to 3 times daily, are expected to last patients an entire month. When used in excess or reduction, problems may occur with pharmacy refills, an addition to financial burdens from buying an increased number of prescription refills. In the absence of good medication compliance and response, patients often have to undergo costly surgical procedures that can place them at an increased risk of infection and loss of vision, while still requiring postoperative management with ophthalmic drops, in addition to being closely monitored by eye care providers.

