In order to ensure patients are receiving the correct amount of drops with each use, there are many drop aid assistive devices available for purchase on the market; however, these drop aids are not routinely offered to our patients because of their unproven cost benefit ratio, and the poorly studied efficacy of the devices. Although, if a drop aid proves to be effective, the cost of the drop aid devices would more than pay themselves through the improvement in medication compliance and visual function of our patients. The “Glaucoma Drop Aid Study” aims to determine if using drop aids during the administration of eye drop medication leads to better results for patients with glaucoma at Boston Medical Center. The implications of this study may show an improved delivery system of ophthalmic medications thus improving medication compliance, visual function, and even decreasing medication waste.

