### 7.2 Subject Exclusion Criteria

An individual who meets any of the following criteria will be excluded from participation in this study:

- Changes glaucoma medication within the past two months or recent glaucoma surgery
- Not a patient of the Boston University Eye Associates

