## 9.2 Day of Enrollment and Randomization

- Subject's IOP and VA will be measured as part of SOC exam
- Dispense study diary
  - Patients will be requested to record the number of days taken to complete the glaucoma medication bottle
- Randomization: After enrollment, subjects will be randomly assigned to Arm A or Arm B, and assigned no device or one of the three drop aid devices
- Subject will be instructed on how to use the drop aid by a member of the research team
- Subject will be requested to administer their drops with the drop aid, or no drop aid if randomized into the control group, with every use
- A member of the research team will confirm the subject's phone number and schedule a time for the 3 week phone call

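### Eligibility fixes the drug for two months but not drop-aid use, so a current aid user enters with an aided baseline IOP, which weakens the paired pre/post test named as primary

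*Combined protocol and SAP*

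**What the plan says.** Section 7.1 requires the patient to be "Currently on the same topical medication for treatment of glaucoma for a minimum of two months". Section 7.2 excludes patients with "Changes glaucoma medication within the past two months or recent glaucoma surgery" and those who are not patients of the practice. The only inclusion item that mentions aids looks forward: "Agrees to use the drop aid with each delivery, return to the clinic after approximately 6 weeks of using the drop aid". Neither section refers to current or past use of an aid, or to who puts the drops in.

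On whether prior use is possible, section 3.1 says that "drop aids are available at local pharmacies for purchase". It then adds that aids are not commonly recommended, because of cost and unproven usefulness. Section 3.2 says "these drop aids are not routinely offered to our patients".

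On conduct, section 9.2 asks subjects to give their drops with the assigned aid, "or no drop aid if randomized into the control group, with every use". Section 5 makes the primary endpoint the comparison of baseline with follow-up IOP. Section 12.3 names a paired t-test, with each patient as his or her own control, as the primary method. Section 12.1.1, by contrast, frames the hypotheses as mean IOP change without a device against mean change with one.

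**The concern.** The two-month window makes a change in IOP attributable to the intervention rather than to a recent change of drug. Here the intervention is the way the drop is delivered, and that is left free at entry. A current aid user assigned to a device swaps one aid for another, so little change is expected. A current aid user assigned to control is asked to stop, so IOP may rise from an aided baseline. Neither change score measures the move from no device to device that the paired test is meant to capture. With ten patients per group, one such patient is 10% of a group.

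**Working it through.** **The plan's own figure.** Section 12.2 gives ten patients in each of four groups: 4 × 10 = 40, which reproduces. The number was set by budget. The plan gives no alpha, power, effect size or SD, so there is no power calculation to check.

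**Inputs.** D is the true IOP reduction from using a study device rather than none. f is the share of enrolled patients already using an aid. The documents give neither. I assume f from 5% to 30%, and that a patient's own aid works as well as a study device.

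**Expected IOP change for each type of patient.**

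| Patient | Device arm | Control, stops own aid | Control, keeps own aid |
|---|---|---|---|
| Not a prior user | -D | 0 | 0 |
| Prior user | 0 | +D | 0 |

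**Arm means.**

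- Device arm: (1-f)(-D) + f(0) = -(1-f)D.
- Control arm, section 9.2 obeyed: (1-f)(0) + f(D) = +fD.
- Between-arm difference, section 9.2 obeyed: -(1-f)D - fD = -D.
- Between-arm difference, controls keep their aid: -(1-f)D - 0 = -(1-f)D.

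At f = 20% the paired device-arm change is -0.8D and compliant controls show +0.2D, while their difference remains -D.

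The equal-efficacy assumption does not drive the third result. If the patient's own aid lowers IOP by E, a prior user changes by -(D-E) on a device and by +E as a compliant control, and the difference is still -D.

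**Cost where the effect is diluted.** This covers the paired device-arm test, and the between-arm test if controls keep their aid. The illustration assumes a two-sided alpha of 0.05, 80% power at f = 0 and an unchanged SD. The multiplier on the number of patients is 1/(1-f)².

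| f | Effect kept | Power | Multiplier |
|---|---|---|---|
| 5% | 95% | 76% | 1.11 |
| 10% | 90% | 71% | 1.23 |
| 20% | 80% | 61% | 1.56 |
| 30% | 70% | 50% | 2.04 |

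**Chance of enrolling at least one prior user**, 1-(1-f)^n:

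| f | Group of 10 | All 40 |
|---|---|---|
| 5% | 40% | 87% |
| 10% | 65% | 99% |
| 20% | 89% | over 99.9% |

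**Chance imbalance.** Take k_d prior users in a device group of ten and k_c in the control group of ten, with controls complying. The difference is -(1 - k_d/10)D - (k_c/10)D = -D + (k_d - k_c)D/10. Each extra prior user on one side therefore moves the contrast by D/10. An excess among controls exaggerates the device effect, and an excess in the device group hides it.

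**The case against.** The strongest reply is that the trial is randomised and section 12.1.1 compares change between arms. For that comparison, prior users who follow section 9.2 do no harm on average, because the masked benefit in the device arm and the worsening in controls offset exactly. This stands. A reader might infer that the device contrast is diluted in general; the instruction in section 9.2 does not support that. Likewise, one control who rises by an assumed 3 mmHg moves the control mean by 3/10 = 0.3 mmHg, but to call this a net bias is to count only one side. It is also small beside sampling error. With an assumed SD of change of 2 to 4 mmHg, the standard error for ten against ten is SD × √(2/10), or about 0.9 to 1.8 mmHg.

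Second, prior use is probably uncommon, on the evidence of sections 3.1 and 3.2. This also stands: the 5% to 30% range is an assumption, and its upper end may be too high.

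Third, a reader might extend the point to patients whose drops are instilled by someone else and want them excluded too. The documents do not support this. Such a patient still has a no-device baseline unless the helper uses an aid, and nothing shows that a device is useless in a helper's hands. Section 3.1 does say "Some patients have difficulty putting in the correct amount of eye drops themselves", but section 3.2 names poor vision and difficulty squeezing the bottle as the problem. Patients who need help may therefore belong to the intended population. Excluding them is a choice of target population, not a correction.

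Finally, it can be said that the root fault is a pre/post test as primary in a randomised trial. That is a separate point. While section 12.3 stands, the paired test is the stated primary analysis, and the offset between arms does not protect it.

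**Conclusion.** The gap is real but narrow. Sections 7.1 and 7.2 admit current drop-aid users, whose baseline IOP is an aided value. The paired device-arm change is then (1-f) of its true value, and compliant controls worsen spuriously by fD. Both results assume that the patient's own aid works about as well as a study device. The between-arm difference keeps its expected value if controls comply, and falls to (1-f) of it if they keep their own aid. The satisfaction survey in section 15.2.4 would not reveal the latter, because its answer options do not separate a study aid from one the patient already owns. Chance imbalance moves a ten-against-ten contrast by D/10 for each patient.

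The actual size cannot be stated, because f and D are unknown and f is probably low. The change is still worth making: it is cheap, it protects the named primary analysis, and it avoids taking an aid away from controls. If prior use goes unrecorded at entry, the problem is hard to repair later.

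**What to change.** Add one exclusion to section 7.2: use of any drop aid device within the past two months, matching the existing medication window. Add the same item to the eligibility form in section 15.2.1 if it is not already there; only part of that form was available for this review, so its absence cannot be asserted.

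Do not exclude patients whose drops are instilled by someone else. Record at baseline who instils the drops, so that the survey answers on missed drops can be interpreted.

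The cost is one screening question and one baseline item. Recruitment is not threatened. Section 3.2 reports "275 glaucoma patients weekly, 80 percent of which are placed on glaucoma medications", which is 275 × 0.80 = 220 treated patients a week, against 40 enrolments in about a year. The downside is that the results will not apply to patients switching from one aid to another.

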### 7.2 Subject Exclusion Criteria

An individual who meets any of the following criteria will be excluded from participation in this study:

- Changes glaucoma medication within the past two months or recent glaucoma surgery
- Not a patient of the Boston University Eye Associates

## 8 Study Intervention

Arm A: No intervention – Control

Arm B: *Active Comparator* – Eye Drop Aids Including:

- Simply Touch Eye Drop Applicator
- Fabrication Autodrop Eye Drop Guide

- Owen Mumford OP 6100 Autosqueeze

Drop Aid devices were funded by a Boston Medical Center grant award. Devices were purchased by the grant award at no cost to the patients. Drop aid devices will be ordered online using the funds provided by the grant award. Upon arrival to Boston Medical Center, drop aid devices will be stored in locked cabinets that only the research team can access. Each drop aid will have a study-specific label indicating it is an investigational device provided by BMC. Administration of the drop aid devices will occur after consenting procedures and randomization to a treatment or control arm. Patients will be instructed by a member of the research team how to use the device. Patients will be expected to use the device each time they administer their eye drops as directed by their provider.

Compliance to drop aid device will be assessed via patient satisfaction surveys. Patient satisfaction surveys ask the participant to confirm the usage of drop aid device after administration of device at the 3 week phone call and 6 week follow-up.

Reference Appendix sections 15.3 for drop aid labels and instructions.

## 9 Study Procedures

See the Appendix section 15.1 for the schedule of events.

The following study procedures will be performed for study-specific purposes:

- Review of inclusion/exclusion criteria for eligibility
- Informed consent
- Study specific medical, ophthalmic, and family history
- Randomization: eligible subjects will be randomized into either Arm A or Arm B, and assigned no device or one of the three drop aid devices
- Completion of phone call satisfaction survey approximately three weeks after enrollment
- Completion of satisfaction survey at follow-up visit approximately six weeks after enrollment
- Collection of information regarding length of medication usage
- Collection of information regarding any AEs, SAEs, or UPs.

The following procedures will be performed as SOC:

- Ophthalmic exam prior to enrollment
- Ophthalmic exam six weeks after enrollment

### 9.1 Screening and Consent

Glaucoma ophthalmology patients who are thought to be eligible for the study based on the eligibility criteria and review of their medical record by the investigator and/or designated study team member will be approached about study participation. The patient's provider (who could be an investigator) will introduce the study to the patient. The provider will alert the investigator (if they are not already an investigator) and/or the designated study team member to assist with enrollment. The following will then be completed by the investigator and/or the designated study team member:

- Review of study inclusion/exclusion criteria
- The consent form will be reviewed with the patient and all study related questions will be answered in a private exam room or consult room.
  - Both the patient and the investigator or the designated study team member conducting the consent form will sign

- The patient will be sent home with a copy of the fully executed consent form
- The patient will also be given the contact information of the principal investigator, clinical research coordinator, and 24-hour emergency number as listed below:

[name]  
Principal Investigator  
[[contact]](mailto:[contact])  
[contact]

[name]  
Clinical Research Coordinator  
[[contact]](mailto:[contact])  
[contact]

BMC Department of Ophthalmology  
Emergency after Hours  
[contact], dial 0 for operator, and ask for on-call ophthalmologist

- Study-specific review of medical record and demographics

## 9.2 Day of Enrollment and Randomization

- Subject's IOP and VA will be measured as part of SOC exam
- Dispense study diary
  - Patients will be requested to record the number of days taken to complete the glaucoma medication bottle
- Randomization: After enrollment, subjects will be randomly assigned to Arm A or Arm B, and assigned no device or one of the three drop aid devices
- Subject will be instructed on how to use the drop aid by a member of the research team
- Subject will be requested to administer their drops with the drop aid, or no drop aid if randomized into the control group, with every use
- A member of the research team will confirm the subject's phone number and schedule a time for the 3 week phone call

## 9.3 Follow-Up Study Visits

### 9.3.1 3 Week Phone Call:

- Subject will complete satisfaction survey for all drop aid treatment or control groups over the phone
- Confirm next SOC clinical visit

### 9.3.2 Final Study Visit: At least 6 Weeks after Enrollment (SOC Clinic Visit)

- Subject will complete a satisfaction survey in person
- Subject's study diary will be collected
- Routine eye exam will be conducted
  - IOP and VA will be checked as part of SOC clinic visit
- Study participation is complete

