## 2 Protocol Summary

Title:	Glaucoma Drop Aid Study
Population:	Male and Female patients of Boston University Eye Associates, 18 or older, having been receiving the same topical medication for treatment of glaucoma for a minimum of two months
Intervention:	Control: 
 
No Glaucoma Drop Aid Device
 
 Drop Aid Devices: 
 
Simply Touch Eye Drop Applicator
 
Fabrication Autodrop Eye Drop Guide
 
Owen Mumford OP 6100 Autosqueeze
 

Objectives:	To determine the efficacy of drop aid devices for improving medication compliance, visual function, and decreasing medication waste for patients at BMC
Design/Methodology:	Arm A: No intervention- Control Arm B: Active Comparator- Eye Drop Aids  Participants will be randomly assigned into one of the study arms. If placed into Arm A, no drop aid device will be assigned. If placed into Arm B, participants will be assigned one of the three drop aid devices (Simply Touch Eye Drop Applicator, Fabrication Autodrop Eye Drop Guide, or the Owen Mumford OP 6100 Autosqueeze).
Total Study Duration:	Approximately 1 year
Subject Participation Duration:	Subject participation length is variable based on appointment wait times and availability. The minimum duration of this study is 6 weeks.

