### 4.2 Study Outcome Measures

The efficiency of various drop aids will be measured through the subject’s glaucoma progression at the end of the study. On the day of enrollment, the subject’s IOP and visual acuity will be measured as part of their standard of care exam. This information is recorded as the baseline exam, and will be compared to measure the patient’s glaucoma progression at the end of the study. Subjects will be required to record the date on which they began each of their glaucoma eye drop bottles, and the date each bottle was finished in a study diary provided by the research team. Subject’s satisfaction will be measured through a brief satisfaction survey approximately 3 weeks after their enrollment. After at least 6 weeks of study participation, subject will be followed up with their regularly scheduled glaucoma provider where they will fill out a second brief satisfaction survey. The study diary will be collected and a routine eye exam will be conducted, with their IOP checked as part of a standard of care clinic visit.

All surveys were created by a member of the research team. The satisfaction survey includes five questions to assess the precision of the drop aid device, overall patient satisfaction, and willingness to use the device long term. The questions are multiple choice questions in which the patient circles the answer that best reflects their response.

Reference Section 12.0 for further statistical analysis explanations.

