## 12 Statistical Plan

### 12.1 Study Hypotheses

#### 12.1.1. Primary Objective: Intraocular Pressure

Formal hypothesis: Drop aids will be cost-effective in delivery of ophthalmic medications by improving baseline IOP measures to six week visit.

Testable hypothesis: Patient baseline IOP measures will be a statistically significant improvement in accordance to the usage of a drop aid device.

Null hypothesis: The patients, who are assigned to a drop aid device baseline IOP measures will not have a statistically significant change with the usage of a drop aid device when compared to patients not assigned to a drop aid device.

Alternate hypothesis: Patients not assigned to a drop aid device will result in larger significant change when compared to patients who are assigned to a drop aid device.

$$H_0: \mu_0 < \mu_d - \delta$$

$$H_A: \mu_0 \geq \mu_d - \delta$$

Where  $\mu_0$ , is the true mean IOP change from baseline to the six week visit without the drop aid device,  $\mu_d$  is the true mean IOP change from baseline to the six week visit with the drop aid device.

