15.2.4 Satisfaction Survey

**Study ID:** \_\_\_\_\_

**Name of study team member completing this form:** \_\_\_\_\_

**Date:** \_\_\_\_\_

**Study Visit:**     3-week phone call         Follow-up clinic visit

1. Do you like the drop aid?
  - a. Yes
  - b. No
  - c. I am not on a drop aid
  - d. I did not use the drop aid
2. Is it easier to instill drops with the help of the drop aid compared without the drop aid?
  - a. Yes
  - b. No
  - c. I am not on a drop aid
  - d. I did not use the drop aid
3. How many times did you miss instilling drops with the help of drop aid?
  - a. None
  - b. 1
  - c. 2
  - d. 3 or more
  - e. I am not on a drop aid
  - f. I did not use the drop aid
4. How many times do you miss instilling drops just using your glaucoma drops?
  - a. None
  - b. 1
  - c. 2
  - d. 3 or more
5. Would you use the drop aid long term?
  - a. Yes
  - b. No
  - c. I am not on a drop aid
  - d. I did not use the drop aid

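### Missed drops are counted with differently worded survey questions that state no recall period, so device and control answers are not like for like

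*Combined protocol and SAP*

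**What the plan says.** **Missed drops.** Section 4.2.2 lists the number of times a patient missed the eye as the first secondary outcome. Section 12.1.2 compares it between patients with and without a device. The survey in Section 15.2.4 is the only instrument for it; the home diary in Section 15.2.3 records only medication names and bottle start and end dates.

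- Question 3 is in the past tense: "How many times did you miss instilling drops with the help of drop aid". Its count options are none, 1, 2 and a top category of three or more, plus options for patients without a device or who did not use it.
- Question 4 asks in the present tense about misses with the bottle alone, with the same four count options. It is the only question on which a control can give a count.
- Neither question names a period. The same form serves the 3-week call and the final visit.

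**Timing of the final survey and IOP.**

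- Section 12.1.1: the control mean "is the true mean IOP change from baseline to the six week visit without the drop aid device". Table 1 in Section 15.1 likewise has a 6-week follow-up column.
- Section 7.1: patients agree to "return to the clinic after approximately 6 weeks of using the drop aid". Section 9 lists "Completion of satisfaction survey at follow-up visit approximately six weeks after enrollment".
- Section 9.3.2: "At least 6 Weeks after Enrollment (SOC Clinic Visit"). Section 4.2: "After at least 6 weeks of study participation, subject will be followed up with their regularly scheduled glaucoma provider".
- Section 2: "Subject participation length is variable based on appointment wait times and availability", and "The minimum duration of this study is 6 weeks".

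No section gives an upper limit or a visit window, and Section 12.3 mentions no allowance for time on study.

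**The concern.** A count can be interpreted only over a known period. Here the period is left to the patient and may differ in two ways.

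1. **Between groups.** Question 3 can reach back only to the day the device was dispensed. Question 4 has no starting point, and under Section 7.1 controls have used the same drops for at least two months. If controls count over a longer period, the device looks better than it is. If they read the question as misses in a typical day or week, it looks worse.
2. **Between patients.** Someone surveyed at 6 weeks and someone surveyed much later may report over very different exposures. Even a patient seen on time may answer for all six weeks or only since the 3-week call.

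The cap adds to this, because once most patients in both groups reach the top category the item can no longer separate them. At stake is the device-versus-control comparison of missed drops, which supports the plan's claims about waste. Nobody will have recorded the period each patient had in mind, so later analysis cannot recover it.

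**Working it through.** **The plan's own figure.** Section 12.2 gives ten patients in each of four groups: 4 × 10 = 40. This was set by budget, with no power calculation, so nothing below changes it.

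**Inputs.** The response categories come from Section 15.2.4. The miss rates are assumptions, because the documents give none; a range is shown. The 12- and 20-week periods are also assumptions, because only the 6-week minimum is stated. Misses are taken as Poisson with mean m = rate × weeks, and patients are assumed to answer for the whole period.

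**Formulas.**

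- Top category: P(X ≥ 3) = 1 − e^(−m)(1 + m + m²/2).
- Score capped at 3: mean = P(1) + 2P(2) + 3P(X ≥ 3).
- Standardised difference: difference in capped means divided by the square root of the average of the two variances.

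**Step 1: unequal periods alone.** Take a device with no effect and 0.5 misses per week in both groups. If controls count over 12 weeks, m = 6 and P = 1 − e^(−6) × 25 = 93.8%. If device users count over 6 weeks, m = 3 and P = 1 − e^(−3) × 8.5 = 57.7%. The spurious gap is 36 points. Halving the period has the same effect on the answers as halving the miss rate.

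**Step 2: the cap, with equal periods and a device that halves the rate.**

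| Period (weeks) | Top category, 0.5 v 0.25 per week | Std. difference, 0.5 v 0.25 | Std. difference, 0.28 v 0.14 | Std. difference, 1.4 v 0.7 |
|---|---|---|---|---|
| 1 | 1.4% v 0.2% | 0.41 | 0.31 | 0.69 |
| 3 | 19.1% v 4.1% | 0.71 | 0.53 | 0.98 |
| 6 | 57.7% v 19.1% | 0.94 | 0.75 | 0.62 |
| 12 | 93.8% v 57.7% | 0.86 | 0.97 | 0.13 |
| 20 | 99.7% v 87.5% | 0.47 | 0.90 | 0.01 |

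Example, 0.5 v 0.25 over 6 weeks: capped means 2.328 and 1.410, variances 0.818 and 1.071, so 0.918 / √0.9445 = 0.94.

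At 14 instillations a week (twice daily, the lower end of the frequency in Section 3.2), 0.28 v 0.14 per week is 2% v 1% of instillations missed, and 1.4 v 0.7 is 10% v 5%.

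**Step 3: reading the table.** At the middle rates the top-category gap is 39 points at 6 weeks, 36 at 12 and 12 at 20, so the collapse comes late. At the lower rates separation is better at 12 and 20 weeks than at 6. At the higher rates it is already falling at 6 weeks and nearly gone at 12.

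**Step 4: choosing a window.** In all three scenarios a 7-day window separates the groups less well than 3 weeks (0.41 v 0.71, 0.31 v 0.53, 0.69 v 0.98), because few misses fall inside one week. For an uncapped Poisson count the standardised difference is (m₁ − m₂) / √((m₁ + m₂)/2). Over 3 weeks this is 0.75 / √1.125 = 0.71 at the middle rates, the same as with the cap, and 2.1 / √3.15 = 1.18 at the higher rates, against 0.98 with the cap.

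**The case against.** **The cap's harm is assumed, not shown.** This stands. A reader might infer that the missed-drops comparison must lose its power as follow-up lengthens. The documents do not support that: they give no miss rate and no visit as late as 20 weeks, and at the lower assumed rates longer follow-up helps.

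**Different periods are not certain.** This also stands. With no stated window, patients may all answer for a recent habitual period. The defect is that the period is unknown, not that it has been shown to differ.

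**The plan already contains some protection.** In part. Randomisation should balance visit dates on average, the 3-week call gives a nominally common time point, and the form's date field lets days on study be derived. None of these aligns question 3 with question 4 or reveals the period a patient had in mind.

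**Variable timing is an open, pragmatic choice.** Fair. Section 2 discloses it. A reader might infer that it biases the IOP result, but the documents give no reason to expect visit timing to differ by group and nothing on how an IOP effect would change after week 6. What remains is that an effect labelled six-week may come from later visits. Restricting the analysis to visits near 6 weeks would shrink groups of ten and select on a post-randomisation variable.

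**Conclusion.** The point holds for missed drops. The two groups are counted by questions that differ in tense and reference, with no recall period, at a final survey bounded only from below. The comparison is therefore not like for like as written. If the counting periods differ twofold at 0.5 misses per week, a device with no effect would show a 36-point gap in the top category. The direction and size in practice cannot be known from the documents.

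Loss of separation through the cap is conditional. It is modest up to 12 weeks at 0.5 v 0.25 per week, absent at 0.28 v 0.14, and severe by 12 weeks at 1.4 v 0.7. All of this rests on Poisson misses, a halving of the rate, and answers covering the whole period.

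For IOP the finding is inconsistent labelling of one visit, not bias. The sample size is unaffected. This is a low-severity point that is worth acting on because the remedy is cheap before data collection and unavailable after it.

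**What to change.** 1. **Survey questions 3 and 4.** Give them parallel wording, differing only in how the drops were instilled, with one explicit recall period that is the same at both contacts and in all groups. The past 3 weeks fits both the 3-week call and the final visit. A 7-day window is not recommended, for the reason in Step 4.
2. **Response format.** Replace the top category with an open numeric count. This matters most if misses are frequent.
3. **IOP visit.** Reconcile Sections 2, 4.2, 7.1, 9, 9.3.2, 12.1.1 and Table 1 on which visit supplies the six-week IOP, and report days from randomisation to that visit by group.

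The cost is a few words on the form and one or two sentences in Section 12, with no added visits or patients. There are three downsides. Patients will make some recall errors over 3 weeks. A call made a few days early would reach back before the device was dispensed. At low and middle miss rates a 3-week count also holds less information than a full count at exactly six weeks (0.71 against 0.94 at the middle rates). That loss buys a period known to be the same for everyone.
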